#### *Statistical Power*

We used data from our historical placebo to estimate power for both the test that uses only patients enrolled in the trial and the test where historical placebo is added. To accomplish this we first randomly sampled 75 placebos from our database. The first 30 are assigned as placebo and their ALSFRS-R values are unchanged. The remaining 60 have their slopes reduced by a fixed percentage of their lme estimated slope and the random error is added back in to simulate real measurements. Next, we test for a treatment effect in the simulated dataset of 90. The simulated data are then combined with the remaining (unsampled) placebo and tested for difference in the placebo subgroups. If this test is not significant (at two-sided  $p<0.05$ ), the combined data are tested for a treatment effect. This procedure was carried out 1000 times, noting the p-values from each simulation. Power was estimated by counting the number of times p-values were less than 0.1 (two-sided test).

These simulations with a treatment effect set to 40% show that with 90 patients at a 2:1 ratio of Memantine to placebo, power was 82% for the test that uses only the 90 patients simulated to be in the trial. Adding historical placebo boosted the power to over 90%.

Because there is a great deal of clinical variability among patients with ALS the major drawback to this study is its small size. A previous study looking at 60 ALS patients performed by Carvalho et al, found no significant improvement in patients randomized to 10 mg BID of Memantine compared to placebo (30). This contradicts the data from our pilot study in which patients' rate of progression was compared both to historical controls and their own baseline rate

of progression. Since it is impossible to identify if a patient is a fast or a slow progressor at randomization, small studies such as Carvalho's, or our previous pilot open label trial, can be skewed if a group of slow progressors are randomized to a placebo arm or a group of fast progressors are randomized to an active arm. We have attempted to modulate these effects somewhat by excluding patients who have had the disease for more than three years as possibly being slow progressors. In addition, we have excluded patients with significantly impaired FVC's, to try to limit the number of fast progressors. These measures are very standard in current ALS trials. Another limiting factor to both Carvalho's and our pilot study is that neither study analyzed the efficacy of Memantine at a higher dose. We feel that by using a higher dose of Memantine a more efficacious response may be seen even in a study which is relatively small. Another limitation to this study is 20mg/bid of Memantine has not been studied in ALS patients. Although 40, 50, 60 and even 80mg/d of Memantine have been studied in numerous other disease states and have been shown to be safe and tolerated, it is still unknown how this population will respond. However, we will assess carefully for safety and adverse events.

To date the most validated tool for assessing outcome of ALS clinical studies remains the ALSFRS-R. This is a subjective assessment of a patient's ability to perform their activities of daily living. Unfortunately, studies looking for a change in ALSFRS-R can be limited by inter-rater reliability and the length of time it takes to see a consistent change in these clinical parameters. If there were a reliable biomarker, which could be correlated to a patient's rate of disease progression, future studies could have a more rapidly assessed objective outcome measure and could stratify an equal number of slow and fast progressors into each treatment arm. Our preliminary data have demonstrated that there are elevated levels of tau and phosphorylated neurofilament heavy chain (pNF-H) in the CSF of patients with ALS as compared to healthy controls (2) suggesting that these proteins could also be used for measuring a patient's disease progression. We have found strong correlation between blood and CSF levels of pNFH and NF-L in ALS patients, and propose that blood levels of these proteins will reflect neurodegeneration in the CNS and provide an easier biofluid for longitudinal sample collection during this next Memantine clinical trial. Recently published data by [name] have also shown a high sensitivity and specificity for the ratio of pNFH/C3 in the CSF for diagnosing ALS (35). We feel these combinations of biomarkers are markers for axonal injury and neuronal cell death. Since motor neurons have very long axons, injury to them can release pNF-H, NF-L and tau into the

CSF, and ultimately the blood. pNFH and NF-L are quite stable and therefore can be measured in the CSF very readily and ultimately in the blood.

In the preliminary results section of this study, we present data from our open label trial of 20 patients with ALS treated with Memantine and Riluzole. This data demonstrated that there was a very strong correlation between a patient's rate of progression and levels of tau and pNF-H in the CSF. Patients who progressed faster than -0.5 ALSFRS-R points per month had an average CSF tau concentration of 574 pg/ml compared to those who progressed at less than -0.5 ALSFRS-R points per month whose CSF tau levels averaged 298 pg/ml (p=0.006). Further, patients in our pilot clinical trial whose CSF tau levels corrected back to that observed in healthy controls exhibited the greatest decline in ALS disease progression, reducing the rate of decline to -0.42 ALSFRS-R points per month. Thus, Memantine may provide neuroprotection as well as decreased levels of phosphorylated cytoskeletal proteins. Therefore, measuring levels of neurofilament in the blood may provide an indirect measure of Memantine drug effects. In addition, recent studies have identified chitinase-1 (Chit-1) as a protein expressed by activated monocytes and microglia and can be measured in the CSF of ALS patients (36). The [name] lab has discovered the Chit-1 levels can also be detected in the blood of ALS patients and levels in the CSF and blood can increase over time in ALS patients (Figure 4 + manuscript in preparation). We propose that blood levels of Chit-1 are a biomarker for peripheral and central inflammation due to monocyte/microglia activation. We will determine the ability of Memantine to reduce Chit-1 levels in the blood before and after Memantine treatment.

Blood samples for biomarker analysis will be collected at Screening, Week 4, Week 12, Week 24 and Week 36. Samples will be collected at a similar time of the day for all subjects to account for daily variability and to standardize the time from the last dose of Memantine. Standard operating procedures will be used for blood collection, processing for plasma and storage at -80C. All samples are coded in order to maintain patient confidentiality and the blinded manner of the biomarker studies. Coded samples will then be batch sent to Barrow Neurological Institute for biomarker analysis. Once the coded samples are batched sent to Barrow Neurological, [name] will assay for pNFH, NF-L, Chit-1 and TNF- $\alpha$  by ELISA.

Phosphorylated neurofilament heavy chain (pNF-H) concentration in blood is determined using a human pNF-H ELISA Kit (Iron Horse Diagnostics, Inc, Phoenix, AZ) in accordance with the

manufacturer's instructions. 10  $\mu$ l of plasma is diluted in 50  $\mu$ l of sample diluent buffer prior to analysis. For the pNFH ELISA, the intra-assay variation is  $\pm 4.0\%$  and the inter-assay variation is  $\pm 8.0\%$ . Purified protein is used as the standard curve. All samples will be analyzed in triplicate within each experiment, and all experiments will be performed at least twice. NF-L levels are measured using the Simoa NF-L assay (Quanterix). Chit-1 levels in blood are determined using a commercially available ELISA kit (LifeSpan BioSciences, Inc, Seattle, WA) in accordance with the manufacturer's instructions. TNF- $\alpha$  levels in plasma are measured using a commercial ELISA kit (R&D Systems, Inc.) following manufacturer's instructions.

We have extensive experience in the proposed methods and have published proper sample collection procedures to maintain protein stability in human biofluids. Therefore, we do not expect any difficulties in collecting coded samples and generating the ELISA results. We anticipate replicating our preliminary findings that blood levels of pNFH and NF-L will decrease in response to Memantine treatment and with the addition of a higher dose (20 mg bid) results will show a greater reduction. We propose that the inflammatory biomarkers including Chit-1 and TNF- $\alpha$  will also decrease during the course of Memantine treatment.

Our previous open-label trial with Memantine employed this same methodology and we have not encountered any problems with the procedures or experimental decline in the levels of these CSF biomarkers. This data would support our hypothesis that Memantine reduces axonal or neuronal injury/damage and thereby reduces pNFH and NF-L levels detected in the blood. Chit-1 levels will be decreased due to reduced peripheral inflammation in response to Memantine. We will correlate the blood levels of each biomarker to clinical measures of ALS disease progression as determined by ALSFRS-R and compare results to placebo.

In order to achieve the third aim of: **Determining if patients who demonstrate characteristics of FTD, illustrate a slowing of behavioral decline on Memantine treatment over the course of the study** we discuss the rationale, designed a study design and discuss possible limitations.

It has been demonstrated that up to half of patients with ALS may develop cognitive impairment during the course of the disease (37) and up to 40% of ALS patients develop frontotemporal dementia (FTD) (38). Despite the relatively high chance of developing FTD, few studies have examined the potential for independent effects on the neuropsychiatric manifestations of this disease. The ALS Cognitive Behavioral Screen (ALS-CBSTM) and the Neuropsychiatric

Inventory Questionnaire (NPI-Q) are two neuropsychological batteries that are validated, brief practical measures that are easily administered and only take about 5 minutes to complete. We feel that given the previous data with Memantine in slowing the progression of behavioral and cognitive decline in other neurodegenerative diseases, such as Alzheimer's, Parkinson's and Lewy Body Disease, that we should study the potential for a positive effect in patients with ALS. The short administration time along with the validity of both scales will be logical additions to this study and should be great indicators of not only the diagnosis frontotemporal dysfunction and even FTD, but also whether Memantine can have any positive effect upon the progression of these changes.

The ALS Cognitive Behavioral Screen (ALS-CBS™), which is a standardized reliable research measure, consists of questions and tasks pertaining to cognition and behavior. The ALS-CBS™ aims to detect frontal lobe-mediated cognitive and behavioral changes and was developed as an initial tool in identifying cognitive and behavioral dysfunction in a clinical setting (39). The ALS-CBS™ measures attention, concentration and mental control. In one study where verbal fluency was used to screen cognition using a cut-off of eight words or less in 1 minute, the sensitivity was 88% but many normal patients scored poorly resulting in a specificity of only 70%. By comparison, the cognitive section of the ALS-CBS™ had a sensitivity of 85% to detect any cognitive impairment and 100% sensitivity to detect ALS-FTD (39). Offering a test battery that takes only 5 minutes, but still illustrates high specificity and sensitivity, will be a reliable outcome measure for determining FTD and the effects of Memantine on patients with cognitive and behavioral impairment (frontotemporal dysfunction).

The Neuropsychiatric Inventory Questionnaire (NPI-Q) a non-ALS specific, validated clinical instrument for evaluating psychopathology in dementia will also be utilized as an outcome measure in this proposal. The NPI-Q provides brief, reliable, informant-based assessments of neuropsychiatric symptoms and associated caregiver distress that may be suitable for use in ALS patients to determine the effectiveness of assessing behavioral changes and how the use of Memantine can be beneficial.

The advantages of using these psychological measurements are to determine the frequency of frontotemporal dysfunction and FTD in our studied patients with ALS. They are sensitive and

reliable tools and can demonstrate the effects of Memantine on slowing the rate of progression of these neuropsychiatric changes.

The ALS-CBS™ and the NPI-Q will be administered at Screening, Week 4, Week 12, Week 24, and Week 36 by each site's study evaluator. These study evaluators who are certified to administer the ALSFRS-R will also administer the neuropsychological questionnaires. Only certified evaluators will be able to administer the questionnaires to limit inter-rater error.

The NPI-Q is given as a two-page questionnaire. The questionnaire consists of 12 symptom domains which the subjects' caregiver are asked to circle "yes" or "no" in response to each screening question, and to either proceed to the next question if the answer is "no" or to rate the symptoms present in the last 4 weeks if the answer is "yes." Neuropsychiatric symptoms are assessed in terms of severity on a three-point scale as (1-mild, 2-moderate, 3-severe), and distress which is based on a 0-5 scale. The total NPI-Q severity score represents the sum of individual symptom scores and ranges from 0 to 36. The total NPI-Q distress score represents the sum of individual symptom scores and ranges from 0 to 60 and tests can be administered in 5 minutes or less.

The ALS-CBS™ questionnaire measures both cognition and behavior. The cognitive section measures attention, concentration, working memory, fluency and tracking, and comprises four subscales with a total score of 20 (lower scores reflect greater impairment). Scoring is based on a combination of scores for each item and the number of errors made. The behavioral section measures empathy, personality, judgment, language and insight. This section includes 15 caregiver rated items that assess changes since disease onset. Items are scored from 0-3 (0 being largest and 3 being no change), total scores range from 0-45.

All of the sites who are participating in this study have previously participated in Neuropsychological ALS studies, therefore the study evaluators are well versed and experienced in administering the NPI-Q. We have good relationships with the physicians and psychologists at California Pacific Medical who have developed the ALS-CBS and therefore we do not expect any difficulties with the administration or the test itself. We anticipate that half of our study population will have characteristics of frontotemporal dysfunction, as previously reported and hope to see an improvement in the rate of progression of subjects with these characteristics over the course of Memantine treatment.

Although our previous open label trial with Memantine did not look at frontotemporal dysfunction of FTD, we do believe that Memantine may be a treatment that would benefit ALS patients with characteristics of FTD since it has been a first line FDA approved treatment for dementia. We will correlate the scores from the ALS-CBS and NPI-Q to clinical measures of ALS disease progression as determined by ALSFRS-R as well as FTD progression and compare results to placebo.

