**I. Purpose, Background and Rationale**

**A. Aim and Hypotheses**

Neuroprotection would be noticeable with respect to reduced neurofilament levels. Neurofilament light chain (NF-L), neurofilament heavy chain (pNFH) are beneficial for diagnosis of ALS and increase at time of symptom onset, and levels of these biomarkers remain relatively constant in the blood and CSF over time during disease progression. Chitinase-1 (Chit-1) and TNF- $\alpha$  are biomarkers for inflammation that are also increased in ALS patients and can be detected in the blood of ALS patients. There is data showing that across a small number of patients the level of NF-L or pNFH remains constant in the blood and CSF (1); so the ability to compare the changes seen in ALS patients treated with Memantine to a control group will be valuable data to prove or refute this observation.

**Aim 1:** The overall challenge is to determine if changes in the levels of specific biomarkers found in blood predict and correlate to the response of high dose Memantine treatment and if this correlates to disease progression. We believe that measurement of specific neuronal proteins and inflammatory proteins in the blood may serve as biomarkers for ALS disease progression. If this hypothesis is correct, then altering the levels of these biomarkers via a drug that modulates axonal/neuronal injury or death may serve as an early indicator of effective therapy.

**Aim 2:** To validate the data from the pilot clinical trial, which suggested that there was a 40% decrease in the disease progression of patients with ALS treated with Memantine. If this study is

also positive, we will have sufficient evidence to move forward with a larger placebo controlled double-blind trial of Memantine at 20 mg in ALS compared to the natural history of ALS.

Obviously, the finding of any medication, in addition to Riluzole and/or Radicava, that slows the progression of the universally fatal disease would serve a tremendous unmet need for this orphan disease.

**Aim 3:** Finally, by using standardized, reliable tools such as the ALS-CBS and the NPI-Q, we will be able to demonstrate if Memantine can improve the neuropsychiatric changes seen in patients with ALS.

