The [name] lab has also observed significantly increased levels of pNFH and NF-L in the blood of ALS patients when compared to healthy controls and disease mimics, including pure upper motor neuron disease and pure lower motor neuron disease (**Figure 2**). These results demonstrate the ability to detect a biomarker of neurodegeneration (neurofilament) in the blood of ALS patients.

**Figure 2: pNFH levels in blood plasma.** Plasma from 87 ALS patients, 50 healthy controls, 44 pure upper motor neuron disease (UMND) and 25 pure lower motor neuron disease ((LMND) disease mimics were used to measure pNFH. The level of pNFH in the plasma of ALS patients was significantly increased versus all other subject groups.

CSF levels of pNFH for 65 ALS subjects were also examined to see if there was a correlation between levels of pNFH and disease survival. These data indicated a clear correlation (Pearson test  $R = -0.485$ ,  $p = 0.016$ ) between pNFH levels and days from symptom onset to death (**Figure 3**). This result suggests that pNFH levels in the CSF are a candidate prognostic biomarker, with higher CSF levels corresponding to more rapid disease progression. Similar results were obtained when pNFH levels were correlated to the rate of clinical disease progression as determined using the ALS Functional Rating Scale - Revised (ALSFRS-R) (Data not shown).

[figure not shown]
These results confirm a prior study that also demonstrated higher CSF levels of pNFH in patients with a more rapid disease progression (15). Rate of disease progression was defined in both studies by the rate of decline in clinical disease parameters (ALSFRS-R measures), with greater than 1.0 unit per month defined as rapid disease progression and less than 1.0 unit per month as slow disease progression. Therefore, blood and CSF levels of pNFH and NF-L have been verified by multiple laboratories as a biomarker for ALS disease progression.

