We propose that therapies to reduce axonal injury would reduce pNFH and/or NF-L levels in the blood and correlate to a reduction in neuronal cell death and increased patient survival. The prior data from a phase II trial for Memantine in ALS patients indicated that reductions in CSF tau levels correlated to slowing of disease progression (2). Sussmuth et al demonstrated that elevated levels of CSF tau were found in patients with ALS (1); however, other studies have not found a strong correlation (16). Therefore, we will not examine tau levels in our current clinical trial.

We feel there is a significant body of literature to support the fact that pNF-H, NF-L, chitinase-1 (Chit-1) and TNF- $\alpha$  may be sensitive biomarkers for neurodegeneration and activation of glial cells and inflammation during ALS. Studies related to neurofilament were noted above. Cereda and colleagues demonstrated that ALS patients exhibit elevated levels of TNF- $\alpha$  and soluble TNFR receptor in the plasma (17). Recent studies have indicated that the chitinase Chit-1 is elevated in the CSF of ALS patients and denotes microglial activation in the spinal cord (18). We also detect significantly increased levels of Chit-1 in the plasma of ALS patients when compared to controls (**Figure 4**).

[figure not shown]
More importantly, we believe based on the open label trial and other previously mentioned studies, that the blood levels of these biomarkers may predict rate of disease progression and monitor effectiveness of Memantine during our upcoming clinical trial. This would offer a number of potential benefits if found to be true. It would allow for a better stratification in future clinical trials as equal number of fast and slow progressors could be randomized into each arm of future studies. This may negate a potential bias against an effective drug if too many rapid progressors are randomized into the active arm. We also believe that if an effective therapy for ALS is found that there may be observed changes in the levels of the blood biomarkers and that these changes may occur as early as four to six months. Therefore, we propose to study the levels and ratios of these

biomarkers at screening and at multiple times during the trial to see if response to therapy can be correlated with rate of disease progression as our preliminary work suggested.

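### Aim 1 asks whether biomarker change marks response to memantine, but the stated analyses (a level–progression correlation and a before/after Chit-1 test) do not test that

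*Combined protocol and SAP*

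**What the plan says.** Section I.A (Aim and Hypotheses) poses two questions about change. One is whether "changes in the levels of specific biomarkers found in blood predict and correlate to the response of high dose Memantine treatment". The other is whether altering the markers "may serve as an early indicator of effective therapy". The same section states an intention: "the ability to compare the changes seen in ALS patients treated with Memantine to a control group will be valuable data". The biomarker rationale in I.C expects that "these changes may occur as early as four to six months".

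Two analyses are then stated, both in the text under Statistical Power in II.C. For every marker: "We will correlate the blood levels of each biomarker to clinical measures of ALS disease progression as determined by ALSFRS-R and compare results to placebo". For Chit-1: "We will determine the ability of Memantine to reduce Chit-1 levels in the blood before and after Memantine treatment". The paragraph with the Chit-1 sentence also says that Chit-1 in CSF and blood can rise over time in ALS. The Statistical Methods subsection covers only ALSFRS-R. No biomarker model, visit, baseline adjustment, significance level or multiplicity rule appears anywhere.

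Samples are scheduled at screening and weeks 4, 12, 24 and 36. Under Remote Enrollment, the screening draw may be omitted, and the Study Table shows no biomarker draw at the baseline visit.

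**The concern.** The aim is about change and response; the stated correlation is about level and progression. Section I.C reports that CSF pNFH is correlated with survival in ALS subjects, with no mention of memantine, and concludes: "This result suggests that pNFH levels in the CSF are a candidate prognostic biomarker". It reports a similar result for ALSFRS-R rate. The pilot results report that pNFH in CSF taken before treatment was associated with faster decline. Section I.A adds that "levels of these biomarkers remain relatively constant in the blood and CSF over time during disease progression". If so, an on-treatment level largely repeats the patient's own starting level, and its correlation with decline is a prognostic link that both arms share whatever the drug does.

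Two further gaps follow. Marker levels and ALSFRS-R decline are taken over the same 36 weeks, and nothing puts marker change ahead of clinical change, which an early indicator needs. And a before/after test of a marker that can rise untreated cannot separate a drug that slows the rise from one that does nothing.

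At stake is the objective in II.A of establishing these markers as outcome measures for later trials. The primary ALSFRS-R comparison is not affected.

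**Working it through.** **1. Inputs, and a check against the plan's own power.** The plan gives no power or significance level for biomarkers, so 5% two-sided is assumed below. Allocation is 60 memantine to 30 placebo (Sample size). The slope effect is 40% of 0.89, or 0.356 points per month. The slope SD is back-calculated from the placebo interval in the open-label results (−0.95 to −0.83, 415 patients): SE = 0.06/1.96 = 0.0306; SD = 0.0306 × √415 = 0.624. With √(1/30 + 1/60) = 0.2236, the primary test at two-sided 10% has power Φ(0.356/(0.624 × 0.2236) − 1.645) = Φ(0.906) = 81.8%. That reproduces the stated 82%. The effect in SD units is 0.356/0.624 = 0.57.

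**2. The plan's correlation.** R = −0.485 is CSF pNFH against days from onset to death. The stated p = 0.016 does not fit the stated 65 subjects, which would give about 0.00004; it fits about 24. With 24, the 95% interval for |r| is tanh(0.5295 ± 1.96/√21), or 0.10 to 0.74. A range of r is therefore used.

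**3. Inert drug: how often is the level–progression correlation significant?** Power ≈ Φ(atanh(r)·√(n−3) − 1.96). For r = 0.485 and n = 60: 0.5295 × 7.550 − 1.96 = 2.04, giving 98%.

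| True r | 60 memantine | 30 placebo | All 90 |
|---|---|---|---|
| 0.3 | 65% | 36% | 82% |
| 0.4 | 89% | 60% | 98% |
| 0.485 | 98% | 79% | 99.9% |

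**4. Working drug: which comparison sees it?** A correlation does not change when a constant is added to either variable. If memantine lowers the marker and improves the slope by the same amount in every treated patient, the within-arm correlation stays where it was, and testing one arm's correlation against the other's has power equal to its significance level. Simulation (10,000 runs per row) with assumed values: baseline level–slope correlation 0.485, marker lowered 0.5 SD, slope improved 0.57 SD, and ρ the correlation between baseline and follow-up marker:

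| Scenario | ρ | Correlation significant on memantine | Arms' correlations differ | Change differs between arms |
|---|---|---|---|---|
| Inert drug | 0.8 | 87% | 5.1% | 4.7% |
| Working drug | 0.7 | 77% | 4.8% | 82% |
| Working drug | 0.8 | 88% | 4.9% | 94% |
| Working drug | 0.9 | 94% | 4.6% | 99.8% |

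Hand check of the last column at ρ = 0.8: the SD of change is √(2 × 0.2) = 0.632; 0.5/0.632/0.2236 = 3.54; Φ(3.54 − 1.96) = 94%.

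**5. What a between-arm test can detect.** At 80% power: (1.96 + 0.842) × 0.2236 = 0.63 SD of change at two-sided 5%, and (1.645 + 0.842) × 0.2236 = 0.56 SD at 10%. The documents give no SD of change, so this cannot be put in concentration units.

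**6. Precision of a later slope.** Placing screening at week 0, the full schedule has 10 ALSFRS-R scores four weeks apart, with sum of squares 16 × 82.5 = 1,320. Weeks 12–36 have 7 scores (16 × 28 = 448) and weeks 24–36 have 4 (16 × 5 = 80). The residual-error SE of a patient's slope rises by √(1,320/448) = 1.7 and √(1,320/80) = 4.1.

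**The case against.** The strongest reply is that this is missing detail, not a wrong choice. The aims say changes will be compared with a control group, I.C says levels and ratios will be followed at several visits, and the correlation sentence ends with a comparison to placebo, which covers Chit-1 too. That stands in part: the intention is there, and the placebo comparison could be read generously. But no method is attached, and read literally the sentence compares correlations, which step 4 shows is insensitive to a uniform effect.

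A drug effect confined to responders could alter a correlation, so the comparison is not blind to every effect. It is weak, however. The detectable Fisher-z difference at 80% power and two-sided 5% is 2.802 × √(1/57 + 1/27) = 0.65, so against 0.485 in one arm the other would need to be about −0.12 or 0.83.

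The evidence for a drug-free correlation is also limited. The coefficient is for CSF and survival, the ALSFRS-R result is not shown, the extension to blood is asserted for pNFH and NF-L, and nothing comparable is shown for Chit-1 or TNF-α. The statement that levels stay constant conflicts with the background and pilot sections, which say pNF-H rises with progression.

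Three stronger readings are tempting and unsupported:

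- **That the trial would probably declare the markers linked to response even if the drug were inert.** This needs a rule that significance within the memantine arm means response. The plan states no such rule, and formally comparing the two correlations gives about 5% false positives. The rates in step 3 show what a significant correlation is worth; they do not predict a report.
- **That the 2:1 allocation would yield a correlation on memantine only.** This needs the same kind of unstated rule.
- **That the Chit-1 problem can be sized from the pilot's rise in CSF tau.** Tau is not measured in this trial, the rise comes from 10 untreated patients, and no size is given for Chit-1 in blood.

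**Conclusion.** The point holds in a limited form. The stated biomarker analyses do not answer Aim 1, and the comparison that would answer it is intended but unspecified. A significant level–progression correlation on memantine is not evidence of response; in the simulation at ρ = 0.8 it appeared in 87% of trials of an inert drug and 88% of trials of a working one. Comparing the arms' correlations has about 5% power against a uniform effect, against about 94% for comparing change between arms (82% to 99.8% for ρ from 0.7 to 0.9).

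The invariance of the correlation under a uniform shift is exact. The percentages rest on the assumed marker shift, the assumed ρ, the 5% level, and the CSF survival coefficient carried over to blood and ALSFRS-R slope. The argument is firmest for the neurofilaments. For Chit-1 the fault is the before/after contrast on a marker said to rise untreated; its size is unknown. The analysis should be changed before unblinding, but the primary efficacy result does not depend on it.

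**What to change.** Replace the two analysis sentences with the following.

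1. **Drug effect.** For each of the four markers, including Chit-1 in place of before/after, test the memantine-minus-placebo difference in log level at one named primary visit, from a repeated-measures model over weeks 4, 12, 24 and 36 adjusted for the screening level. State the significance level, a multiplicity rule for four markers, and how remote enrollees without a screening sample are handled, since their first scheduled sample is at week 4, on treatment. Week 24 is the only scheduled sample inside the four-to-six-month window the plan expects.
2. **Early indicator (exploratory).** Relate change from screening to week 12 to the ALSFRS-R slope over weeks 12–36, adjusted for screening level and arm. Treat the week 24 version as supportive only.
3. **Prognosis.** Report the level–progression correlation under that label, not as evidence of response.

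**Cost.** A little more analysis work, with no new visits or samples. The later-slope analysis is less precise (residual-error SE about 1.7 times the full schedule from week 12, about 4.1 times from week 24). Week 12 also falls before the window in which the plan expects change, so a null result there would not rule out a later signal.
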